6.3.5 Time to Dialysis

Using the IAS, the number and percentage of subjects who started dialysis will be reported along with the Kaplan-Meier estimates for the quartiles of the distribution for time to dialysis.

Additionally, a Kaplan-Meier plot and a listing of the derived time to dialysis values will be presented.

Time to dialysis is defined as the time in months from the first REACT injection to the start of dialysis. Subjects who did not start dialysis during the study will be censored as of their last visit date.

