**Table 4: Summary of Classification and Prevalence Estimates for CKD**

Stage*	Description	GFR (mL/min/1.73m  )
1	Kidney damage with normal or increased GFR	≥90
2	Kidney damage with mild decrease in GFR	60-89
3	Moderate decrease in GFR	30-59
4	Severe decrease in GFR	15-29
5	Kidney failure	<15 (or dialysis)

\* Source: National Kidney Foundation, 2002. National Kidney Foundation. 2002. KDOQI clinical practice guidelines for chronic kidney disease: evaluation, classification, and stratification. *Am J Kidney Dis.* 39:S1-266.

All-cause mortality rates were shown to increase as GFR declined; mortality rates were highest at Stages 4-5 of CKD. Populations defined as having an eGFR <60 mL/min/1.73m^2 consistently exhibited a higher mortality rate than comparator groups where there was no evidence of CKD.

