9. SAMPLE SIZE

Up to 10 subjects who complete screening procedures and satisfy all inclusion and exclusion criteria will be enrolled. Statistical analyses will be primarily descriptive in nature and no statistical hypothesis testing is planned for the study.

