10. DIFFERENCES BETWEEN SAP AND PROTOCOL

In this SAP, we have specified that the secondary endpoint analysis for eGFR will use three CKD-EPI equations [2009 CKD-EPI serum creatinine equation, 2012 CKD-EPI cystatin C equation, and 2012 CKD-EPI serum creatinine-cystatin C equation] For the exploratory analysis of eGFR only the 2009 CKD-EPI serum creatinine equation will be used. This is done to ensure consistency with all other REACT studies. A protocol clarification letter dated 25May2021 was issued to clarify that the CKD-EPI 2009 Creatinine equation will be used for analyses rather than the CKD-EPI 2012 Creatinine-Cystatin C based equation.

The efficacy analyses as specified in [section 6](#) of this SAP are consistent with the objectives and endpoints section of the protocol. This differs slightly from the primary versus secondary endpoint identification in the statistical section of the protocol.

The exploratory endpoint of time to dialysis was added to this SAP. This endpoint is of clinical interest, but was not previously specified in the protocol.

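### If any subject dies before a later dialysis start, the Kaplan-Meier analysis of time to dialysis will overstate the cumulative incidence of dialysis, because deaths are censored (low severity)

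*SAP*

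**What the plan says.** SAP 6.3.5 works in the injection analysis set, which is every subject with at least one injection. There, "the number and percentage of subjects who started dialysis will be reported along with the Kaplan-Meier estimates for the quartiles", and a Kaplan-Meier plot and a listing of the derived times are added. The clock is defined so: "Time to dialysis is defined as the time in months from the first REACT injection to the start of dialysis". The censoring rule is "Subjects who did not start dialysis during the study will be censored as of their last visit date". Death and transplant are not named. No competing-risk method, cumulative incidence or dialysis-or-death composite appears in 6.3.5 or among the protocol differences in SAP 10.

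On the weight of the endpoint, SAP 10 states: "The exploratory endpoint of time to dialysis was added to this SAP". On size, SAP 9 states: "Up to 10 subjects who complete screening procedures and satisfy all inclusion and exclusion criteria will be enrolled", and it adds that "no statistical hypothesis testing is planned for the study".

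On the population, Protocol 5.1 requires an eGFR of 14 to 20. By the protocol's Table 4 that is Stage 4 with the top edge of Stage 5. The text under that table says that "mortality rates were highest at Stages 4-5 of CKD", without giving a rate. Protocol 6.7 lists death among the ways a subject's participation can end.

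**The concern.** Kaplan-Meier treats a censored subject as having the same future risk of the event as those still under observation. That suits a subject who leaves alive. A subject who has died cannot start dialysis, yet the method passes that subject's share of risk to the survivors, so every later dialysis start makes a larger step than it should. One minus Kaplan-Meier then estimates dialysis risk in a setting where nobody dies, not the proportion of these subjects who reach dialysis.

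At stake is whether the curve and quartiles describe what happened. SAP 6 drops measurements taken after dialysis starts from the efficacy analyses, so 6.3.5 is where dialysis itself is summarised as an outcome. In an unfavourable case the same output could show a median time to dialysis as reached while the crude percentage beside it says that fewer than half the subjects started.

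**Working it through.** **Inputs from the documents.** At most 10 subjects (SAP 9). Two injections 6 months apart, then 24 months of follow-up (SAP 3.1), so T = 6 + 24 = 30 months = 2.5 years from the first injection for a subject given both. Neither document states a dialysis rate, a death rate or an expected event count, so there is no figure of the plan's own to reproduce. All rates below are assumptions.

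**Step 1: constant hazards.** Let h be the dialysis hazard and d the death hazard.

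- Kaplan-Meier with death censored: 1 − exp(−hT)
- Cumulative incidence: h/(h + d) × [1 − exp(−(h + d)T)]

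With h = 0.25 per year, Kaplan-Meier gives 1 − exp(−0.625) = 46.5% at 30 months.

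| d per year | Cumulative incidence | Overstatement (points) |
|---|---|---|
| 0.03 | 0.25/0.28 × (1 − exp(−0.700)) = 44.9% | 1.5 |
| 0.05 | 0.25/0.30 × (1 − exp(−0.750)) = 44.0% | 2.5 |
| 0.10 | 0.25/0.35 × (1 − exp(−0.875)) = 41.7% | 4.8 |
| 0.20 | 0.25/0.45 × (1 − exp(−1.125)) = 37.5% | 9.0 |

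The last column is taken before rounding. As a second range, fix the 30-month Kaplan-Meier risk and let annual death probability run from 3% to 15%. The overstatement is then 1.0 to 5.0 points at a risk of 30%, 1.6 to 8.0 at 50%, and 2.1 to 10.2 at 70%.

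**Step 2: ten subjects, four dialysis starts, everyone else followed to 30 months.** The cumulative incidence is 40% throughout and equals the crude percentage. One minus Kaplan-Meier depends on the order of events:

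- No deaths, or all deaths after the last dialysis start: 40.0%.
- One death, first: 1 − (8/9)(7/8)(6/7)(5/6) = 1 − 5/9 = 44.4%.
- Two deaths, in the order death, dialysis, death, then three dialysis starts: 1 − (8/9)(6/7)(5/6)(4/5) = 49.2%.
- Three deaths, in the order death, dialysis, death, dialysis, death, dialysis, dialysis: 1 − (8/9)(6/7)(4/5)(3/4) = 54.3%.

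Over all 15 orderings of four dialysis starts and two deaths, the result runs from 40.0% to 50.0%, with mean 45.6%.

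**Step 3: the quantities that the SAP tabulates.** SAP 6.3.5 tabulates quartiles, not a 30-month risk. Take each quartile as the first time the curve reaches 25% or 50%. In the two-death example above, Kaplan-Meier steps through 11.1, 23.8, 36.5 and 49.2%, and the cumulative incidence through 10, 20, 30 and 40%. Both reach 25% at the third dialysis start and neither reaches 50%, so no reported quartile changes. Counting all orderings:

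- One death: neither the first quartile nor the median ever changes.
- Two deaths: each changes in 1 of 15 orderings. That is the one with both deaths first, where Kaplan-Meier steps through 1/8, 2/8, 3/8 and 4/8 and just touches 25% and 50%.
- Three deaths: the median changes in 18 of 35 orderings (51%).

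**Step 4: sampling error.** The exact 95% interval for 4 of 10 is 12% to 74%.

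**The case against.** The strongest reply is that this hardly matters here. The endpoint is exploratory, was added in the SAP, has no comparator and supports no test or decision rule. The crude percentage starting dialysis is reported beside the Kaplan-Meier estimates and is not inflated by censored deaths. The listing gives every subject's time, and SAP 7.2.5 tabulates fatal adverse events. Early deaths may also be few. Protocol 5.1 limits age to 30 to 65, and 5.2 excludes a life expectancy under 2 years, incapacitating heart or lung disease, and most cancers within 3 years. All of this stands, and it keeps the severity low. It does not remove the point: the curve and quartiles carry no note about deaths, and nothing links the adverse event tables to this analysis.

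A reader might infer three stronger things that the documents do not support.

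- **That the analysis will overstate dialysis risk.** It will do so only if a death without dialysis precedes a later dialysis start.
- **That the protocol's remark on mortality establishes a large bias.** The remark ranks CKD stages and gives no rate for a population selected as this one is. At death hazards of 0.03 to 0.05 per year the gap is 1.5 to 2.5 points.
- **That transplant before dialysis must be a competing event.** Protocol section 2 treats dialysis and transplant together as the renal replacement therapy to be delayed. Coding transplant as a competing event would take one form of that outcome off the curve. The SAP has to make this choice and state it.

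**Conclusion.** The point holds in conditional form and is of low severity. The rule in SAP 6.3.5 censors deaths before dialysis by implication, and no other section corrects this. One minus Kaplan-Meier is therefore at least as large as the cumulative incidence of dialysis, and the quartiles are the same or earlier. The 30-month overstatement of about 1.5 to 9 points rests on assumed constant hazards (dialysis 0.25 per year, death 0.03 to 0.20 per year) and on 30 months of follow-up for every subject. None of the rates comes from the documents. Even the upper end is small against an interval as wide as 12% to 74%. With four dialysis starts among ten subjects, the tabulated quartiles almost never move with one or two deaths, while with three the median moves in about half the orderings.

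**What to change.** In SAP 6.3.5:

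- Estimate the cumulative incidence of dialysis by Aalen-Johansen, with death before dialysis as a competing event. Take the plot and the quartiles from it, and report a quartile as not reached when the curve stays below it.
- Flag deaths before dialysis on the plot and in the listing of derived times.
- If Kaplan-Meier is kept, alone or alongside, label it as a cause-specific estimate with death censored.
- State whether a transplant before dialysis counts as part of a renal-replacement endpoint or as a competing event, consistent with the protocol's aim of delaying dialysis or transplant.

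Estimates at fixed times are optional. The cost is a few lines of SAP text and a standard procedure, with no new data beyond the dates of death and transplant. The output is slightly less familiar. If nobody dies before a later dialysis start, and transplants do not enter, the numbers are the same as under the present plan.

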7. SAFETY ANALYSIS

Safety assessments will include adverse events, clinical laboratory assessments, vital signs, imaging, pregnancy test, and ECG. Safety evaluation will be performed according to the schedule of events presented in the [Appendix A-B](#). No hypothesis testing will be performed.

7.1 Biopsy and REACT Injections

The number of subjects biopsied, total number of injections received, and the total volume of REACT injected will be summarized and presented for the FAS. All biopsy and injection data will be listed for the FAS.

7.2 Adverse Events

An adverse event (AE) is the development of an undesirable medical condition (including abnormal laboratory findings) or the deterioration of a pre-existing medical condition following or during exposure to a study treatment, whether or not considered to have a causal relationship with study procedures or the investigational product. The Investigator is responsible for ensuring that all AEs observed by the Investigator or reported by the subject that occur from the day of the biopsy procedure through 24 months after the final injection of REACT are monitored and recorded in the subject's medical record as well as the CRF.

7.2.1 Treatment-Emergent Adverse Events

Treatment-emergent adverse events (TEAEs) are defined as any AE that started after the first injection of REACT or started prior to the first injection but increased in severity or frequency after the first injection of REACT. For missing onset or end dates, the rules stated in [Section 4.8](#) will be followed. The imputed dates will be used to determine if the AE is treatment emergent.

In addition to the overall treatment-emergence period defined above, the analysis periods defined in [section 4.9](#) will be used for analysis of the AEs:

7.2.2 Adverse Event Intensity

Intensity will be assessed by the Investigator using the "Common Terminology Criteria for Adverse Events" (CTCAE) version 4.03, from the US National Cancer Institute^[6] (refer to http://evs.nci.nih.gov/ftp1/CTCAE/CTCAE_4.03_2010-06-14_QuickReference_8.5x11.pdf).

If an AE is not included in the CTCAE, then the Investigator will determine the intensity of the AE according to the following criteria:

- **Mild (Grade 1):** The AE is noticeable to the subject but does not interfere with routine

activity.

- **Moderate (Grade 2):** The AE interferes with routine activity but responds to symptomatic therapy or rest.
- **Severe (Grade 3):** The AE significantly limits the subject's ability to perform routine activities despite symptomatic therapy. Severe events are usually incapacitating.
- **Life-Threatening (Grade 4):** The subject is at immediate risk of death.
- **Death (Grade 5)**

If the intensity is missing, then the adverse event is assumed to be grade 5.

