7.2.3 Adverse Event Relationship to Investigational Product or Procedure

An Investigator listed on Form FDA 1572 may make the determination of relationship to the biopsy, REACT injection procedure or REACT investigational product for each AE. Definitions of relatedness categories are:

- **Not Related:** Exposure to the study treatment did not occur, or the occurrence of the AE is not reasonably related in time, or the AE is considered unlikely to be related to the study treatment.
- **Unlikely Related:** The study treatment and the AE were not closely related in time, and/or the AE could be explained more consistently by causes other than exposure to the study treatment product.
- **Possibly Related:** The study treatment and the AE were reasonably related in time, and the AE could be explained equally well by causes other than exposure to the study treatment product.
- **Related:** The study treatment and the AE were reasonably related in time, and the AE was more likely explained by exposure to the study product than by other causes, or the study treatment was the most likely cause of the AE.

For the purpose of safety analyses, all AEs judged by the Investigator to be “possibly related” or “related” will be considered treatment-related adverse events. If relationship to biopsy, REACT injection, or REACT product is missing, then the adverse event is assumed to be related for analysis purposes.

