7.2.5 Adverse Event Summaries

All AEs (serious and non-serious) will be classified by SOC and PT using MedDRA.

For AEs, the following will be summarized and presented for the IAS. Note that summaries of treatment-emergent AEs only apply to the IAS as all subjects in the IAS have been treated. Summaries of AEs during the pre-injection period apply to both the IAS (treated) and FAS (biopsied). Firstly, the overall summary of AEs and summaries for the pre-injection period will be presented for the IAS. If there are more subjects in the FAS (biopsied) than the IAS (treated), then the overall summary of AEs and the pre-injection period tables will be presented for the FAS as well.

An overall summary of –AEs will be presented, which includes:

- a. the number and percentage of subjects experiencing an AE in pre-injection period
- b. the number and percentage of subjects experiencing a TEAE during the acute first injection, inter-injection, acute second injection, post-second injection, and post-injection periods
- c. the number and percentage of subjects experiencing an AE by greatest intensity in pre-injection period
- d. the number and percentage of subjects experiencing a TEAE by greatest intensity during the acute first injection, inter-injection, acute second injection, post-second injection, and post-injection periods
- e. the number and percentage of subjects experiencing an AE related to biopsy during the pre-injection period
- f. the number and percentage of subjects experiencing a TEAE related to biopsy during the acute first injection, inter-injection, acute second injection, post-second injection, and post-injection periods
- g. the number and percentage of subjects experiencing a TEAE related to REACT investigational product during the acute first injection, inter-injection, acute second injection, post-second injection, and post-injection periods
- h. the number and percentage of subjects experiencing a TEAE related to REACT injection procedure during the acute first injection, inter-injection, acute second injection, post-second injection, and post-injection periods
- i. the number and percentage of subjects experiencing an SAE during the pre-injection period

- j. the number and percentage of subjects experiencing a treatment emergent SAE (TESAE) during the acute first injection, inter-injection, acute second injection, post-second injection, and post-injection periods

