- k. the number and percentage of subjects experiencing a TEAE leading to study discontinuation during the acute first injection, inter-injection, acute second injection, post-second injection, and post-injection periods
- l. the number and percentage of subjects experiencing a TEAE leading to death during the acute first injection, inter-injection, acute second injection, post-second injection, and post-injection periods

In the overall summary of AEs table, besides tabulating the number and percentage of subjects, the total number of AE episodes will also be provided. If a subject has repeated episodes of a particular AE, all episodes will be counted in the summary table.

Additionally, each of the categories of events presented in the overall summary of AEs table will be summarized by SOC and PT in individual tables. In the remaining summary tables, the incidence of TEAEs will be calculated by dividing the number of subjects who have experienced the event by the total number of subjects in the analysis set. Thus, the incidence of TEAEs is shown in terms of the total number of subjects and not in terms of the total number of episodes. If a subject has repeated episodes of a particular TEAE, only the most severe episode, or the episode with the strongest causal relationship to biopsy, REACT product, or REACT injection procedure will be counted in the summary tables.

A subject with more than one type of TEAE in a particular SOC will be counted only once in the total number of subjects experiencing TEAEs in that particular SOC. Since a subject could have more than one type of TEAE within a particular SOC, the sum of subjects experiencing different TEAEs within the same SOC could appear greater than the total number of subjects experiencing TEAEs in that SOC. Similarly, a subject who has experienced a TEAE in more than one SOC will be counted only once in the total number of subjects experiencing AEs in those SOCs.

All AEs will be presented in tables in descending order from the SOC with the highest incidence to the SOC with the lowest incidence. Within each SOC, AEs will be sorted in descending order from the PT with the highest incidence to the PT with the lowest incidence.

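### SAP 7.2.2 imputes Grade 5, which the section defines as death, for any adverse event with missing intensity, so a survivor can be counted at Grade 5

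*SAP*

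**What the plan says.** SAP 7.2.2 has the investigator grade intensity by CTCAE version 4.03 and gives a written five-level scale for events the CTCAE does not cover. The highest level that a subject can survive is "Life-Threatening (Grade 4"); Grade 5 is death. The section ends: "If the intensity is missing, then the adverse event is assumed to be grade 5". This sentence applies to every AE, whatever its outcome or seriousness. Protocol 8.2.1 has the same scale and no rule for missing intensity.

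SAP 7.2.3 has a parallel rule for causality: "If relationship to biopsy, REACT injection, or REACT product is missing, then the adverse event is assumed to be related for analysis purposes".

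SAP 7.2.5 uses the grade in these places:

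- Item c: "the number and percentage of subjects experiencing an AE by greatest intensity in pre-injection period".
- Item d: "the number and percentage of subjects experiencing a TEAE by greatest intensity", for each of five post-injection periods.
- System organ class and preferred term tables: "each of the categories of events presented in the overall summary of AEs table will be summarized by SOC and PT in individual tables".
- Repeated episodes in those tables: "If a subject has repeated episodes of a particular TEAE, only the most severe episode" is counted, or the episode with the strongest causal relationship.

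Item l separately reports "the number and percentage of subjects experiencing a TEAE leading to death". The SAP does not name the variable from which item l is derived.

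**The concern.** The two worst-case rules look alike but differ in one respect. Any AE can be related, so imputing a relationship gives a value that could be true. An event the subject survived cannot be Grade 5 on the SAP's own definition, so the intensity rule can assign an impossible value. The imputed grade is one step too high for every non-fatal event.

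The consequence is a survivor appearing in the death row of the intensity tables. In a safety study of up to 10 treated subjects, a reader would notice a single Grade 5 entry and take it at face value. The entry might also disagree with item l in the same overall table. If item l were programmed from the grade, the disagreement would disappear and a fatal TEAE that did not happen would be tabulated.

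The rule also sits uneasily with SAP 4.5, which says that missing data are left missing and not imputed. SAP 7.2.2 departs from this without a cross-reference.

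**Working it through.** The plan gives no figure to reproduce. The check applies the rule to a simple case.

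**Inputs**

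- Missing intensity is set to 5, and Grade 5 is death (SAP 7.2.2).
- Subjects are counted at their greatest intensity (SAP 7.2.5, items c and d).
- The incidence denominator is all subjects in the analysis set (SAP 7.2.5).
- At most 10 subjects are treated (Protocol Synopsis, Sample Size).
- Assumptions: no deaths, and one non-fatal TEAE with blank intensity at lock. The documents give no rate of blanks.

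**Step 1: one subject.** Take a survivor with one recorded Grade 2 event and one blank. Greatest intensity is the maximum over the subject's events.

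- Current rule: max(2, 5) = 5.
- Recorded grades only: 2.
- Non-fatal blanks capped at Grade 4: max(2, 4) = 4.

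If the two are episodes of the same event, the most-severe-episode rule lets the imputed 5 displace the recorded 2 in the preferred-term intensity table as well.

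**Step 2: size.** Percentage points at Grade 5 per affected survivor = 100 × 1/n.

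- n = 10 (documented maximum treated): 10.0
- n = 8 (assumed): 12.5
- n = 5 (assumed): 20.0

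The pre-injection tables are also produced for all biopsied subjects when that set is larger than the injected set. Biopsied subjects who are not injected may be replaced, so that denominator could exceed 10 and the step would then be below 10.0 points.

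**Step 3: agreement with item l** (n = 10, no deaths, one blank non-fatal TEAE):

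| Rule and source of item l | Grade 4 from the blank | Grade 5 | Item l |
|---|---|---|---|
| Current; item l from a death indicator | 0/10 | 1/10 (10.0%) | 0/10 |
| Current; item l from grade = 5 | 0/10 | 1/10 (10.0%) | 1/10 (10.0%) |
| Proposed; item l from a death indicator | 1/10 (10.0%) | 0/10 | 0/10 |

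The first line is internally inconsistent. The second is consistent but false. The SAP does not say which would apply.

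**Step 4: spread.** The periods in SAP 4.9 are nested: the acute first-injection period lies within the inter-injection period, which lies within the post-injection period. One blank TEAE in the first month after the first injection therefore puts the subject at Grade 5 in three columns of item d and in the matching class and term tables.

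**The case against.** The strongest reply is that the rule may never operate. Protocol 8.3 requires the investigator to record intensity for each AE. SAP 4.1 requires source verification and query resolution before lock, and a missing grade among so few subjects is easy to chase. Nothing formal depends on the result either: the analyses are descriptive, the primary endpoint does not use grade, and the pausing rules in Protocol 8.6 rest on actual deaths and investigator judgement. The listings carry the collected data, so a blank can be traced. All of this stands and keeps the point minor. It does not make the rule right. The sentence operates only when a blank remains, and it then miscounts every non-fatal event it touches. Double programming will not catch this, because both programmers follow the same sentence.

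A second reply is that deriving item l from the grade is conjecture. That is fair. Item l is worded like item k, on discontinuation, and probably rests on a separate field. The second line of the table is a possibility left open by the SAP's silence, not a prediction.

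A third reply is that Grade 4 may also overstate a trivial event, and that a separate row for missing intensity would fit SAP 4.5 better. That alternative is legitimate. Grade 4 is preferred here because it keeps the sponsor's worst-case approach and removes only the value that cannot be true.

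**Conclusion.** The concern holds. SAP 7.2.2 conflicts with its own definition of Grade 5, and nothing elsewhere in the SAP or protocol corrects it. The effect is zero if no intensity is blank at lock. Otherwise each affected survivor adds 10.0 percentage points to the Grade 5 row when 10 subjects are treated, and more when fewer are. This rests on at least one non-fatal AE keeping a blank intensity after queries are resolved, and the documents do not allow the likelihood of that to be estimated. Severity is minor: the error is confined to the intensity tables, with a possible knock-on to item l, and leaves the primary endpoint untouched.

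**What to change.** Replace the last sentence of SAP 7.2.2 with:

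> An AE with missing intensity is assigned Grade 5 only if it is recorded as having resulted in death; otherwise it is assigned Grade 4, the highest non-fatal grade. The number of AEs with imputed intensity is given in a footnote.

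In SAP 7.2.5, state that item l is derived from the same death indicator, for example the death criterion among the SAE criteria in SAP 7.2.4. It would also help to note in SAP 4.5 that AE intensity is an exception to the no-imputation rule.

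The cost is one replaced sentence, one clause for item l, and a footnote on the overall AE summary and on each greatest-intensity table by class and term. No new rows, tables or data collection are needed. If the sponsor prefers a separate row for missing intensity, that also removes the false Grade 5 count, at the price of an extra row and of giving up the worst-case approach.
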